Study Protocol

Protocol Title: Cranial electric stimulation (CES) to modify suicide risk factors in psychiatric inpatients

Study No.: HP-00065640, Date 6th February 2016

Principal Investigator: [name] MD, [contact], [contact] (24 hour access)

Brief Summary

This pilot study aims to investigate whether a treatment called cranial electric stimulation or CES can decrease risk factors for suicide. The specific CES device we will use is called Alpha-Stim®. CES will be used in addition to usual treatment (medication and group therapy).

Detailed Description

Suicide is still a major issue in the United States and all around the world. There are many reasons for people attempting suicide and the major modifiable risk factors are depression, anxiety, insomnia, and agitation. The standard treatment for all suicidal patients includes medication, admission to a hospital and reducing the risk factors. Medications have potential side effects and concerns about the drug interactions. One of the biological treatment alternatives to medication is cranial electric stimulation. This technique uses a device to stimulate the brain through electrical current. Using an Alpha-Stim® device, current is applied to the brain using skin electrodes which can be easily clipped on to the earlobe. The amount of current used is very low and is 1/1000th of the current used for electroconvulsive therapy (ECT) and 1/10th to 1/20th of the 1-2 milli amperes used with transcranial direct current stimulation (tDCS). Our goal is to examine the safety and efficacy of this device when used as an add-on or adjunctive treatment to the usual treatments during the inpatient stay.

Study Type: Interventional

Study Phase: 4

Study Design

Allocation: Randomized Intervention Model: Parallel Assignment

Masking: Double Blind (Participant, Care Provider, Investigator, Outcomes Assessor)

Primary Purpose: Treatment

Conditions:

- Suicide
- Depression

- Anxiety
- Insomnia
- Agitation

Intervention Device: Alpha-Stim®. Study Arms • Experimental: Adjunctive CES

CES 100µA for one hour daily, five to seven days per week. Rating scales will be administered at baseline (i.e., pre-treatment), twice a week and at the end of the study.

Intervention: Device: Alpha-Stim®.

Sham Comparator: Sham control CES

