For the sham group the Alpha-Stim® will not emit electricity. All other procedures will be the same for both the sham group and the active CES group. The current intensity will be preset and locked by the manufacturer. The sham devices will appear identical to the active device.

Intervention: Device: Alpha-Stim

Primary Outcome Measures:

Change in the modifiable suicide risk factors (MSRF's)

To assess the efficacy of adjunctive cranial electric stimulation (CES), specifically Alpha-Stim®, to reduce suicide risk in psychiatric inpatients through a randomized, double-blind, sham-controlled, clinical trial. The primary efficacy outcome measure will be change in the modifiable suicide risk factors (MSRF's) as indicated by a summed global score from rating scales measuring the MSRFs that include depression (Montgomery-Åsberg Depression Rating Scale), anxiety (Hamilton Anxiety Rating Scale), insomnia (The Pittsburgh Sleep Quality Index) and agitation (Agitated Behavior Scale).

Assess adverse effects and safety

To assess safety of adjunctive cranial electric stimulation (CES), specifically Alpha-Stim®, to reduce suicide risk in psychiatric inpatients through a randomized, double-blind, sham-controlled, clinical trial. The primary safety outcome measure will be responses to an adverse effect assessment questionnaire (GASE questionnaire).

Secondary Outcome Measures:

Assess length of stay

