Random forest model predicting Pittsburg Sleep Quality Index score change between the final observation and baseline (PSQI\_Delta).

% variation explained: 13.01%

[figure not shown]
- Meaning that ~87% of the variation is unexplained

Here is the plot showing how the model is converging. Better.

Here are the experimental variables that are explaining the most variation or are the most predictive of the PSQI\_Delta score. It is encouraging that MADRA\_Delta score is one of the best predictors of PSQI\_Delta score.

rf

[figure not shown]
Random forest model predicting Length of Stay (LOS).

% variation explained: 18.7%

- Meaning that ~81% of the variation is unexplained

[figure not shown]
Here is the plot showing how the model is converging.

[figure not shown]
Here are the experimental variables that are explaining the most variation or are the most predictive of the LOS.

rf

[figure not shown]

[figure not shown]
[figure not shown]
I made some box plots of the target variables with notches. If the notches are overlapping that means that the difference is not significant.

MADRA\_Delta

HAMAT\_Delta

I also ran some linear models on the target variables to see if there was a significant proportion of the variation explained by the treatment. Here are the various models. A summary of the results is that none of the target variables explained a significant proportion of the variance in the treatment variable. In addition the treatment variable did not explain a significant proportion of the variance in any of the target variables.

Active vs Sham

```
Call:
lm(formula = dat$Active_vs._Sham ~ dat$MADRA_Delta + dat$PSQI_Delta +
    dat$LOS + dat$HAMAT_Delta)

Residuals:
    Min       1Q   Median       3Q      Max
-0.7116 -0.4783  0.1233  0.4296  0.6952

Coefficients:
                Estimate Std. Error t value Pr(>|t|)
(Intercept)    1.680905   0.272114   6.177 1.85e-06 ***
dat$MADRA_Delta -0.008970   0.014086  -0.637   0.530
dat$PSQI_Delta  0.024970   0.021857   1.142   0.264
dat$LOS        -0.014567   0.011225  -1.298   0.206
dat$HAMAT_Delta 0.006887   0.019592   0.352   0.728
---
Signif. codes:  0 '***' 0.001 '**' 0.01 '*' 0.05 '.' 0.1 ' ' 1

Residual standard error: 0.5104 on 25 degrees of freedom
Multiple R-squared:  0.1317,    Adjusted R-squared:  -0.007216
F-statistic: 0.9481 on 4 and 25 DF,  p-value: 0.4529
```

MADRA\_Delta

```

Call:
lm(formula = dat$MADRA_Delta ~ dat$HAMAT_Delta + dat$PSQI_Delta +
    dat$Active_vs._Sham + dat$LOS)

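### The protocol's primary safety outcome (GASE) is not compared between active and sham in any analysis in the available SAP text

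*SAP*

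**What the plan says.** The protocol's Detailed Description gives safety equal standing with efficacy: "Our goal is to examine the safety and efficacy of this device". Under Primary Outcome Measures, the entry on adverse effects and safety names the measure: "The primary safety outcome measure will be responses to an adverse effect assessment questionnaire (GASE questionnaire". The trial is randomised, double-blind and sham-controlled, so the design supplies a comparator for adverse effects as well as for symptoms.

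The SAP section headed Random forest results reports five forests, mentions notched box plots of the target variables, and then turns to regression: "I also ran some linear models on the target variables", with the stated aim of seeing whether treatment accounts for a significant share of their variation. Five linear models are printed. The conclusion on treatment is: "In addition the treatment variable did not explain a significant proportion of the variance in any of the target variables". GASE, adverse effects and safety are not mentioned anywhere in the SAP text from Method onwards.

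**The concern.** These are analyses already run, with output printed. The gap is therefore a named primary outcome that does not appear among the results, and more than a detail left for later specification.

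As far as the available text goes, the reader receives a non-significance statement about three symptom scales and length of stay, with nothing beside it on adverse effects. Two things are at stake. An imbalance in adverse effects between active and sham would not be visible in these analyses. And a general statement that treatment explained nothing significant could be taken as reassurance about harm, although no harm variable was among those tested.

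**Working it through.** **1. Is GASE in any available analysis?** The forests have five targets: treatment arm, MADRA_Delta, HAMAT_Delta, PSQI_Delta and LOS. The linear models use the same five variables, and every formula is printed in full (the first two begin "lm(formula = dat$Active_vs._Sham ~ dat$MADRA_Delta + dat$PSQI_Delta" and "lm(formula = dat$MADRA_Delta ~ dat$HAMAT_Delta + dat$PSQI_Delta"):

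| Outcome | Predictors | GASE present? |
|---|---|---|
| Arm | MADRA_Delta, PSQI_Delta, LOS, HAMAT_Delta | No |
| MADRA_Delta | HAMAT_Delta, PSQI_Delta, arm, LOS | No |
| HAMAT_Delta | MADRA_Delta, PSQI_Delta, arm, LOS | No |
| PSQI_Delta | MADRA_Delta, HAMAT_Delta, arm, LOS | No |
| LOS | MADRA_Delta, PSQI_Delta, arm, HAMAT_Delta | No |

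The output can be relied on as printed. The treatment t values reproduce as estimate divided by standard error on 25 df:

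- MADRA_Delta: −1.77929/2.79430 = −0.637 (p = 0.530)
- HAMAT_Delta: 0.71411/2.03158 = 0.352 (p = 0.728)
- PSQI_Delta: 1.98695/1.73926 = 1.142 (p = 0.264)
- LOS: −4.3329/3.3387 = −1.298 (p = 0.206)

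The SAP's conclusion is thus correct for those four variables, and it extends to no others.

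**2. How many patients per arm?** The available text does not state the split, but the arm regression implies it.

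- Patients: 25 residual df + 5 coefficients = 30.
- Residual sum of squares: 0.5104² × 25 = 6.513.
- Total sum of squares: 6.513/(1 − 0.1317) = 7.50 (7.499 to 7.502 allowing for rounding).
- For a two-valued arm variable one unit apart, the total is n₁n₂/30. A 15/15 split gives 7.500; a 14/16 split gives 7.467 and is excluded.
- Check on one-unit coding: the two MADRA/arm coefficients multiply to (−0.008970) × (−1.77929) = 0.0160, which equals t²/(t² + 25) = 0.637²/(0.637² + 25) = 0.0160.

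These 30 are the patients in the printed models. The number randomised and the number who had at least one session are not given.

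**3. What could a by-arm GASE summary show at this size?** The documents give no GASE data, so the rates and counts below are illustrative.

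- Chance of seeing an adverse effect at least once among 15 patients, 1 − (1 − p)¹⁵: 54% at a true rate of 5%, 79% at 10%, 96% at 20%.
- Exact two-sided 95% upper limit for 0 of n, 1 − 0.025^(1/n): 21.8% for n = 15. If the safety population differs, it is 30.8% for n = 10 and 16.8% for n = 20.
- Newcombe 95% interval for the difference with 3/15 in each arm: −28 to +28 percentage points.
- Fisher exact test, two-sided: 5/15 versus 0/15 gives p = 0.042; 4/15 versus 0/15 gives p = 0.10. With no events under sham, five events under active is the smallest count that crosses 0.05, before any allowance for looking at several adverse effects.

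A table would therefore probably reveal common adverse effects, but it could not rule out sizeable rates or differences.

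**The case against.** The strongest objection is that the SAP text before its Method heading is not available. A GASE summary could be there, and material missing for that reason cannot be counted as missing from the plan. This stands, and it limits the conclusion.

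Second, the forest inputs and importance plots are not shown, so GASE variables may have been predictors in the forest for treatment arm, which reports a 60% out-of-bag error. That also stands as a statement of what is unknown. It would not close the gap, however: the SAP itself says the importance numbers have no significance threshold, and an importance rank or a classification error gives no adverse-effect rate by arm.

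Third, the SAP reads as a report of particular analyses and nowhere claims to be the complete set. That is fair. It argues for asking whether a safety analysis exists elsewhere, but it does not make the available results cover safety.

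Fourth, the numerical illustrations would apply to any study with 15 per arm. This is true. They show what a table could and could not deliver, and they do not measure harm in this trial.

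A reader might infer more: that the trial leaves its safety objective unanswered, or that an excess of adverse effects would go unreported. With part of the SAP unavailable, the documents do not support either statement for the SAP as a whole.

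**Conclusion.** The point holds for the available text. The protocol makes GASE the primary safety outcome. None of the ten available models has GASE as an outcome, nothing in the text describes an active-versus-sham comparison of it, and the stated conclusion on treatment is confined to three symptom-change scores and length of stay. Whether a GASE analysis exists in the unavailable part of the SAP cannot be determined.

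No bias or error rate can be attached to the omission, because there are no GASE data to work from. What can be sized is the information a summary would carry: with about 15 patients per arm, 0/15 leaves rates up to about 22% open, and equal counts of 3/15 leave differences of about 28 points either way open. It follows that a non-significant GASE comparison would not be evidence of safety either.

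This rests on three assumptions: that GASE was administered as the protocol intends, that the safety population is close in size to the 30 modelled patients, and that the unavailable SAP text does not already contain the analysis.

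**What to change.** First confirm whether the SAP text before Method contains a by-arm GASE analysis. If it does not, add a descriptive one:

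- Population: all randomised patients who had at least one session, by arm, with the number stated.
- Content: number and percentage with any adverse effect, and by item if the questionnaire is itemised (the protocol text does not describe its structure).
- Precision: exact 95% intervals within each arm, and a 95% interval for the active-minus-sham difference.
- Placement: beside the efficacy conclusion, so that the non-significance statement is not read as covering harm.
- Interpretation: state that a sample of this size can only bound adverse-effect rates, giving the limit for zero events at the actual number per arm, and that a non-significant difference is not evidence of safety.

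If GASE was collected as specified, the cost is one table and a paragraph, with no further visits or patients. If collection was incomplete, the number with responses in each arm should be reported. The downside is that the intervals will be wide and will support only a weak statement about safety.

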### **Random forest results:**

[figure not shown]
All random forest models were run to create 2001 trees.

*Random forest model predicting treatment group (Active vs Sham)*

[figure not shown]
OOB (out-of-bag) error rate: 60%

- This means that the model was wrong 60% of the time and correct 40% of the time.

Here is a plot showing how the model is converging as the number of trees increases. Overall this is the inverse of what you would want to see. Optimally you want the error to start high and decrease to a convergence or a plateau as the number of trees increases. The convergence is settling at an error of  $\sim 0.6$ , which is your OOB error rate.

[figure not shown]

For reference this is what a more favorable plot looks like. This plot has an OOB error rate of 5.73%.

Back to your data, here are the experimental variables that are most predictive of treatment group. There are 2 accuracy metrics here that are used interchangeably based on the preference of the investigator. The accuracy numbers are a bit arbitrary and there is no threshold of significance per se. These are simply the most predictive variables of the target experimental variable.

rf

[figure not shown]
*Random forest model predicting Montgomery-Asberg Depression Scale change between the final observation and baseline (MADRA\_Delta)*

The MADRA\_Delta score is continuous; therefore, the model produces a % variation explained rather than an OOB error rate.

[figure not shown]
% variation explained: 14.14%

- Meaning that ~85% of the variation is unexplained

Here is the plot showing how the model is converging. Again the model is not converging very well.

Here are the experimental variables that are explaining the most variation or are the most predictive of the MADRA\_Delta score. It is encouraging that HAMAT\_Delta score and PSQI-Delta score are two of the best predictors of MADRA\_Delta score.

[figure not shown]

*Random forest model predicting Hamilton Depression Score change between the final observation and baseline (HAMAT\_Delta)*

% variation explained: 0.83%

[figure not shown]
- Meaning that ~99% of the variation is unexplained

Here is the plot showing how the model is converging. Again the model is not converging very well.

Here are the experimental variables that are explaining the most variation or are the most predictive of the HAMAT\_Delta score. It is encouraging that MADRA\_Delta score is one of the best predictors of HAMAT\_Delta score.

rf

[figure not shown]

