Residuals:
    Min       1Q   Median       3Q      Max
-19.1440  -4.4362   0.3207   4.8098  13.4379

Coefficients:
                Estimate Std. Error t value Pr(>|t|)
(Intercept)    -4.75714    4.17875  -1.138  0.265741
dat$HAMAT_Delta  0.84571    0.21889   3.864  0.000703 ***
dat$PSQI_Delta  0.65285    0.28752   2.271  0.032044 *
dat$Active_vs._Sham1 -1.77929    2.79430  -0.637  0.530071
dat$LOS         -0.07574    0.16263  -0.466  0.645431
---
Signif. codes:  0 '***' 0.001 '**' 0.01 '*' 0.05 '.' 0.1 ' ' 1

Residual standard error: 7.188 on 25 degrees of freedom
Multiple R-squared:  0.5498,    Adjusted R-squared:  0.4778
F-statistic: 7.633 on 4 and 25 DF,  p-value: 0.0003661

```

HAMAT\_Delta

```

Call:
lm(formula = dat$HAMAT_Delta ~ dat$MADRA_Delta + dat$PSQI_Delta +
    dat$Active_vs._Sham + dat$LOS)

Residuals:
    Min       1Q   Median       3Q      Max
-10.2459  -2.5605   0.1305   1.8374  11.9851

Coefficients:
              Estimate Std. Error t value Pr(>|t|)
(Intercept)   -5.84565    2.86952  -2.037 0.052353 .
dat$MADRA_Delta  0.44207    0.11442   3.864 0.000703 ***
dat$PSQI_Delta  -0.05453    0.22805  -0.239 0.812978
dat$Active_vs._Sham1 0.71411    2.03158   0.352 0.728154
dat$LOS         0.26534    0.10549   2.515 0.018688 *
---
Signif. codes:  0 '***' 0.001 '**' 0.01 '*' 0.05 '.' 0.1 ' ' 1

Residual standard error: 5.197 on 25 degrees of freedom
Multiple R-squared:  0.5646,    Adjusted R-squared:  0.4949
F-statistic: 8.104 on 4 and 25 DF, p-value: 0.000247

```

PSQI\_Delta

```

Call:
lm(formula = dat$PSQI_Delta ~ dat$MADRA_Delta + dat$HAMAT_Delta +
    dat$Active_vs._Sham + dat$LOS)

Residuals:
    Min       1Q   Median       3Q      Max
-11.3494  -2.1282   0.1626   1.9709   9.8305

Coefficients:
              Estimate Std. Error t value Pr(>|t|)
(Intercept)    0.65390    2.71122    0.241  0.811
dat$MADRA_Delta  0.26188    0.11534    2.271  0.032 *
dat$HAMAT_Delta -0.04184    0.17500   -0.239  0.813
dat$Active_vs._Sham1 1.98695    1.73926    1.142  0.264
dat$LOS        -0.04182    0.10311   -0.406  0.688
---
Signif. codes:  0 '***' 0.001 '**' 0.01 '*' 0.05 '.' 0.1 ' ' 1

Residual standard error: 4.553 on 25 degrees of freedom
Multiple R-squared:  0.2684,    Adjusted R-squared:  0.1513
F-statistic: 2.293 on 4 and 25 DF,  p-value: 0.08759

```

LOS

```

Call:
lm(formula = dat$LOS ~ dat$MADRA_Delta + dat$PSQI_Delta + dat$Active_vs._Sham +
    dat$HAMAT_Delta)

Residuals:
    Min       1Q   Median       3Q      Max

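### The SAP's conclusion on treatment rests on three separate scale changes and length of stay, so it cannot stand as the result for the protocol's primary outcome, the change in the four-scale summed score

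*SAP*

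**What the plan says.** **Protocol, Primary Outcome Measures.** There is one primary efficacy outcome: "The primary efficacy outcome measure will be change in the modifiable suicide risk factors (MSRF's) as indicated by a summed global score". Its components are the Montgomery-Åsberg depression scale, the Hamilton Anxiety scale, and "insomnia (The Pittsburgh Sleep Quality Index) and agitation (Agitated Behavior Scale". Length of stay appears under Secondary Outcome Measures: "Assess length of stay".

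**SAP, Random forest results.** The forests predict treatment group, MADRA_Delta, HAMAT_Delta, PSQI_Delta and LOS. The five linear models use the same five variables, each in turn regressed on the other four. Two of the calls begin "lm(formula = dat$MADRA_Delta ~ dat$HAMAT_Delta + dat$PSQI_Delta" and "lm(formula = dat$HAMAT_Delta ~ dat$MADRA_Delta + dat$PSQI_Delta"; arm and LOS are the remaining terms. The sentence that introduces these models draws the conclusion on treatment: "In addition the treatment variable did not explain a significant proportion of the variance in any of the target variables".

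The forest for HAMAT_Delta is headed "Random forest model predicting Hamilton Depression Score change between the final observation and baseline (HAMAT\_Delta", although the Hamilton component in the protocol is the anxiety scale.

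**The concern.** The trial asks whether CES changes the combined burden of four modifiable risk factors, and the protocol fixes the quantity that answers this: one sum and one change. The visible SAP draws its conclusion from other quantities. Three of the four components are modelled separately, each adjusted for the others, and the fourth target is a secondary outcome.

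Non-significance on several component models is not a result for their sum. Component differences can cancel or accumulate, and the precision of the sum depends on how the components correlate. The printed treatment coefficients are also conditional on the other post-baseline outcomes, so they cannot be added to give the contrast for the sum. A reader who takes the summary sentence as the efficacy result would have neither an estimate nor an interval for the outcome that the protocol made primary, and nothing on agitation.

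**Working it through.** **1. The documents side by side**

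| Quantity | Protocol role | Outcome of a visible forest or linear model? |
|---|---|---|
| Change in four-scale sum | Primary efficacy | No |
| Depression change | Component | Yes (MADRA_Delta) |
| Anxiety change | Component | Yes, if HAMAT is the anxiety total |
| Insomnia change | Component | Yes (PSQI_Delta) |
| Agitation change | Component | No |
| Length of stay | Secondary | Yes (LOS) |

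**2. Reproducing the SAP's own figures.** With t = estimate/SE and a two-sided p on 25 df, the treatment rows give:

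- MADRA_Delta: -1.77929/2.79430 = -0.637, p=0.530
- HAMAT_Delta: 0.71411/2.03158 = 0.352, p=0.728
- PSQI_Delta: 1.98695/1.73926 = 1.142, p=0.264
- LOS: -4.3329/3.3387 = -1.298, p=0.206

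All four agree with the printout. The 25 residual df plus 5 parameters give n=30.

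**3. Recovering the unadjusted differences.** Five variables, each regressed on the other four, determine the inverse K of their matrix of sums of squares and products:

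- K_ii = 1/(25 × RSE_i²)
- K_ij = -b_ij × K_ii

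Consistency check on the MADRA–HAMAT entry:

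- From the MADRA model: -0.84571/(25 × 7.188²) = -6.547 × 10⁻⁴
- From the HAMAT model: -0.44207/(25 × 5.197²) = -6.547 × 10⁻⁴

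The other pairs agree equally well. Inverting K gives an arm sum of squares of 7.50, which is 15 × 15/30, so 15 patients per arm. The cross-products with arm are -10.0 (MADRA), -11.0 (HAMAT) and 14.5 (PSQI). Dividing each by 7.50 gives the unadjusted difference, level 1 minus level 0:

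| Outcome | Printed, mutually adjusted | Unadjusted (p) |
|---|---|---|
| MADRA_Delta | -1.78 | -1.33 (0.72) |
| HAMAT_Delta | +0.71 | -1.47 (0.59) |
| PSQI_Delta | +1.99 | +1.93 (0.29) |

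**4. The sum of the three visible scales**

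- Difference: (-10.0 - 11.0 + 14.5)/7.5 = -6.5/7.5 = -0.87
- Total sum of squares: 2869.10 + 1550.63 + 708.36 + 2 × (1409.01 + 643.79 + 239.19) = 9712.07
- Residual SD: √[(9712.07 - 6.5²/7.5)/28] = 18.62
- SE: 18.62/√7.5 = 6.80
- 95% CI on 28 df: -14.8 to 13.1, p=0.90

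Adding the printed coefficients instead gives -1.78 + 0.71 + 1.99 = +0.92. The contrast for the sum therefore cannot be read off the tables.

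**5. What a three-scale sum could detect.** Assuming two-sided alpha 0.05 and 80% power (the visible documents state neither): (1.96 + 0.84) × 18.62 × √(2/15) ≈ 19 points.

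**6. Adding agitation, by assumption only.** The visible text gives no agitation mean, SD or correlation. I assumed agitation differences from -10 to +10, an SD of 3 or 6, and a correlation with the three-scale sum of 0 or 0.5. The four-scale p-value then runs from about 0.13 to 0.92.

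**The case against.** **Not all of the SAP was available.** The part before Method could hold an analysis of the summed score or of agitation. This stands. A reader might infer that the SAP never addresses its primary objective, but the documents as seen support only the statement that the visible analyses and the quoted sentence do not.

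**Agitation may appear in a forest.** No predictor list is printed for any forest, and the importance plots are not shown. Agitation could be a predictor there, so it would be wrong to say that it is in no model. What can be checked is that it is no forest's named target and is in no printed formula.

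**The sentence is modest.** It reports non-significance for listed variables. It does not say that CES has no effect, and it does not mention the primary objective. Analysing LOS is legitimate because it is a secondary outcome, and nothing says that it was substituted for agitation. All of this stands, and it is also why the sentence cannot serve as the primary result.

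**The answer might not change.** The three-scale sum has p=0.90, the differing signs of the components are within noise, and no agitation scenario tried above gave p below 0.12. A reader might infer that an effect lies hidden in the sum; the documents do not support that.

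**Adjustment is a separate matter.** The move of HAMAT from +0.71 to -1.47 comes from dropping the other post-baseline outcomes as covariates, not from summing. That is correct. It matters here only because it shows that the printed tables do not yield the missing estimate.

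**Conclusion.** The point holds for the visible text. The SAP's statement on treatment concerns three scale changes and LOS. The protocol's primary outcome is a four-scale sum, and no visible analysis has that sum, or an agitation change, as its outcome. The statement therefore cannot be used as the primary efficacy result. If the unavailable part of the SAP does analyse the sum, the statement still needs to be reconciled with that result.

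In size, the part that can be recovered is a difference of -0.87 (95% CI -14.8 to 13.1): no sign of a difference, but an interval too wide to exclude differences of more than 10 points either way. This rests on the printed regressions sharing one set of 30 patients, which their mutual agreement supports; on an unweighted sum; and on HAMAT being the anxiety total. The text does not say which arm is level 1, so the sign cannot be read as favouring either arm. The agitation contribution is unknown. The defect is a missing estimate for the primary outcome; the documents do not show that the non-significant reading is wrong.

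**What to change.** 1. Confirm that HAMAT is the Hamilton Anxiety total, and correct the forest heading if it is.
2. For each patient, compute the change from baseline to final observation in the protocol's summed score (MADRS + HAM-A + PSQI + Agitated Behavior Scale). State that the sum is unweighted, or give the weighting, because the protocol text does not spell this out.
3. Report the active-minus-sham difference in that change with its 95% CI as the single primary efficacy result, without the other post-baseline outcomes as covariates. State which arm is coded 1.
4. Base the efficacy conclusion on that result. Reword the summary sentence so that it names the variables it covers.
5. Report the four component changes, including agitation, as supporting results and LOS as secondary.

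The cost is one derived variable and one extra model on scales that the protocol already specifies. If the Agitated Behavior Scale is missing for some patients, the primary result will rest on fewer than 30; the number should be given.

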-12.844  -4.353  -2.341   2.845  23.249

Coefficients:
              Estimate Std. Error t value Pr(>|t|)
(Intercept)    20.0404    3.3876   5.916 3.57e-06 ***
dat$MADRA_Delta  -0.1136    0.2438   -0.466  0.6454
dat$PSQI_Delta  -0.1563    0.3854   -0.406  0.6885
dat$Active_vs._Sham1 -4.3329    3.3387   -1.298  0.2062
dat$HAMAT_Delta  0.7611    0.3026    2.515  0.0187 *
---
Signif. codes:  0 '***' 0.001 '**' 0.01 '*' 0.05 '.' 0.1 ' ' 1

Residual standard error: 8.802 on 25 degrees of freedom
Multiple R-squared:  0.3168,    Adjusted R-squared:  0.2075
F-statistic: 2.898 on 4 and 25 DF,  p-value: 0.04239

```

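### The SAP's linear-model conclusion on treatment is a bare non-significance statement from 30 patients; it should be arm differences with 95% intervals, read as inconclusive

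*SAP*

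**What the plan says.** The Protocol's Brief Summary sets the aim: "This pilot study aims to investigate whether a treatment called cranial electric stimulation or CES can decrease risk factors for suicide". Its primary efficacy outcome is the change in a summed score of four scales (depression, anxiety, insomnia, agitation). Length of stay is secondary.

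The SAP, under Random forest results, fits five linear models and summarises them in two statements. The first concerns the model with arm as the response: "none of the target variables explained a significant proportion of the variance in the treatment variable". The second is the treatment conclusion: "In addition the treatment variable did not explain a significant proportion of the variance in any of the target variables".

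The printed treatment rows are:

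- MADRA_Delta: "dat$Active_vs._Sham1 -1.77929 2.79430 -0.637 0.530071"
- HAMAT_Delta: "dat$Active_vs._Sham1 0.71411 2.03158 0.352 0.728154"
- PSQI_Delta: "dat$Active_vs._Sham1 1.98695 1.73926 1.142 0.264"
- LOS: estimate -4.3329, SE 3.3387, t -1.298, p 0.2062

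Each of these models also contains the other two change scores and LOS or, in the LOS model, all three change scores. No visible text gives an interval for the arm difference, a difference worth detecting, or a comment on precision.

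**The concern.** A p-value above 0.05 says only that zero is compatible with the data. With few patients, many other values are compatible too, and only an interval shows which. The useful product of a pilot is the estimate and its precision. A verdict of non-significance discards both and can be read as evidence that CES has no effect. Anyone planning a larger trial from this report would get no effect size, no interval and no usable standard deviation from the stated conclusion.

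**Working it through.** **1. Reproduce the printed tests.** With t = estimate/SE on 25 df, two-sided:

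- MADRS: -1.77929/2.79430 = -0.637, p = 0.530
- HAM-A: 0.71411/2.03158 = 0.352, p = 0.728
- PSQI: 1.98695/1.73926 = 1.142, p = 0.264
- LOS: -4.3329/3.3387 = -1.298, p = 0.206

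All four agree with the SAP, so its sentence is correct as far as it goes.

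**2. Sample size.** The MADRA_Delta model prints "Residual standard error: 7.188 on 25 degrees of freedom" and the LOS model "Residual standard error: 8.802 on 25 degrees of freedom". Adding 5 coefficients to 25 df gives n = 30. In the model with arm as response, the total sum of squares is 25 × 0.5104² / (1 - 0.1317) = 7.50. A 15:15 split gives 30 × 0.25 = 7.50.

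**3. Intervals for the coefficients as printed.** Estimate ± 2.060 × SE, level 1 minus reference level:

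- MADRS: -1.8 (-7.5 to +4.0)
- HAM-A: +0.7 (-3.5 to +4.9)
- PSQI: +2.0 (-1.6 to +5.6)
- LOS: -4.3 (-11.2 to +2.5)

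These are conditional on other outcomes measured after randomisation, so they are not intervals for the overall arm difference.

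**4. Treatment-only differences.** Five variables, each regressed on the other four, determine the inverse covariance matrix. Its diagonal is 1/s² and its off-diagonal is -b/s², where s² = (residual SE)² × 25/29 and b is the printed coefficient. Each off-diagonal entry can be computed from two models, and all pairs agree to rounding. For example, MADRS with HAM-A, leaving out the common factor 25/29: 0.84571/7.188² = 0.01637 and 0.44207/5.197² = 0.01637.

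Inverting the matrix gives an arm variance of 0.2586, which matches 15:15 (7.5/29 = 0.2586). The difference is cov(outcome, arm)/0.2586. Its SE is the pooled SD × √(2/15), and the 95% interval uses t = 2.048 on 28 df.

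| Outcome | Cov. with arm | Difference | Pooled SD | SE | 95% CI | CI in SD |
|---|---|---|---|---|---|---|
| MADRS change | -0.345 | -1.3 | 10.10 | 3.69 | -8.9 to +6.2 | -0.88 to +0.62 |
| HAM-A change | -0.379 | -1.5 | 7.40 | 2.70 | -7.0 to +4.1 | -0.95 to +0.55 |
| PSQI change | 0.500 | +1.9 | 4.93 | 1.80 | -1.8 to +5.6 | -0.36 to +1.14 |
| LOS (days) | -1.448 | -5.6 | 9.64 | 3.52 | -12.8 to +1.6 | -1.33 to +0.17 |

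The half-width is 2.048 × √(2/15) = 0.75 SD for every outcome. HAM-A changes sign between steps 3 and 4 (+0.7 to -1.5), so the choice of covariates matters. Solving the model intercepts for the means gives a mean stay of 13.4 days, against which the LOS interval can be judged.

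**5. Power with 15 per arm.** Two-sided 5%, noncentral t on 28 df, noncentrality d × √(15/2):

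- d = 0.5 (noncentrality 1.37): 26%
- d = 0.8 (2.19): 56%
- d = 1.06 (2.90): 80%

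A 0.5 SD effect would therefore be missed 74% of the time and a 0.8 SD effect 44% of the time.

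**The case against.** The best defence is that the sentence is literally right and that the SAP nowhere says CES is ineffective. Each model prints an estimate, SE and df, so a reader can form an interval. The SAP also says that notched box plots were drawn, and these show some uncertainty around medians. On this view the point is one of wording.

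Much of that stands. No false statement is alleged, and precision is not wholly hidden. But the intervals a reader can form directly are those of step 3, which answer a conditional question. Notches are not an interval for the arm difference, and the visible text does not say which arm is level 1.

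Three stronger readings are tempting, and the documents do not support them:

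- **Large differences remain open in both directions.** Taking 0.8 SD as large, no outcome has that much open on both sides. For LOS and PSQI the near limit is 0.17 and 0.36 SD.
- **Non-significance was likely even if the effect were large.** Power at 0.8 SD is 56%, so significance would have been slightly the more likely result. The statement holds for a moderate effect.
- **This is the SAP's only treatment conclusion.** The SAP also reports the regression with arm as response, a 60% out-of-bag error for predicting arm, and a reading of the notches. The SAP text before the Method section was not available. The point is therefore limited to the linear-model conclusion in the visible text.

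**Conclusion.** The concern holds in this limited form. The linear-model conclusion on treatment reports non-significance without an interval, from a sample that cannot separate no effect from imprecision. On every modelled outcome the treatment-only interval includes zero and extends to 0.9 to 1.3 SD on one side and 0.2 to 0.6 SD on the other. The far ends do not all have the same sign (negative for MADRS, HAM-A and LOS, positive for PSQI), and without the arm label none can be called benefit or harm. The supportable reading is inconclusive.

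Assumptions:

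- The rebuild uses rounded printed output.
- HAMAT is taken as the protocol's Hamilton Anxiety scale, although the SAP's text labels it a depression score.
- LOS is taken to be in days.
- Significance is taken as two-sided 5%, as the printed tests imply.
- Sizes are in SD units, because the documents give no clinically relevant difference.

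**What to change.** Replace the summary sentence with the active-minus-sham difference and its 95% interval for each outcome, stating which arm is which level. Take these from treatment-only or baseline-adjusted models that exclude the other change scores and LOS as covariates. Running confint on the printed models is not enough.

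Report the protocol's summed risk-factor score first, since no visible model analyses it, then each component scale including agitation, then LOS. State that the pilot is inconclusive where the interval includes both zero and differences of the size shown above, and do not present non-significance as the finding.

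The cost is a few extra model fits in R and less definite wording. No new data are needed, provided that the agitation scale was recorded as the protocol specifies.
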